12.2.5. Recording Adverse Events

All reported AEs will be documented, including events that are spontaneously reported by a subject and/or parent/guardian. AEs may also be elicited by asking each subject (and/or parent/guardian) a general, non-directed question such as "How are you feeling?" or "How have you been feeling since the last visit?" Directed questioning and examination will then be done, as appropriate. Generally, in this population, AEs should be elicited from the parent/guardian in consultation with the subject.

A full description of reaction(s) including body site and severity, as well as the criterion (or criteria) for regarding the report as serious, if applicable, should be given. In addition to a description of the reported signs and symptoms, whenever possible, attempts should be made to establish a specific diagnosis for the reaction. Whenever feasible, the AE should be documented as a medical diagnosis (highest possible level of integration). When this is not possible, the AE should be documented in terms of the signs and/or symptoms observed by the Investigator and/or reported by the subject and/or parent/guardian.

Information documented will include the diagnosis or succinct description of the AE, the date of onset and the date of resolution (if applicable), severity, seriousness, relationship to IP, action taken with respect to IP, and the outcome. It is the responsibility of the Investigator to document all AEs that occur, in accordance with the guidelines above, whether or not they are considered to be related to the IP. AEs will be reported from the time of signing the ICF and, if applicable, the subject assent form, and through the End of Trial Visit.

The Investigator is responsible for reporting AEs and SAEs to the reviewing IRB/IEC in accordance with the IRB/IEC's standard procedures.

12.2.6. Adverse Event Severity

The severity of each AE/SAE will be assessed according to the Common Terminology Criteria for Adverse Events (CTCAE) Dictionary, Version 5.0, which is available for download: https://ctep.cancer.gov/protocoldevelopment/electronic_applications/docs/CTCAE_v5_Quick_R_eference_8.5x11.pdf. which provides the following scale:

- **Grade 1/Mild**; asymptomatic or mild symptoms OR clinical or diagnostic observations only OR intervention not indicated
- **Grade 2/Moderate**; minimal, local or noninvasive intervention indicated OR limiting age- appropriate instrumental activities of daily living
- **Grade 3/Severe** or medically significant but not immediately life-threatening; hospitalization or prolongation of hospitalization indicated OR disabling OR limiting self care activities of daily living
- Grade 4/Life-threatening consequences OR urgent intervention indicated
- Grade 5/Death related to AE

It remains important to distinguish between serious and severe AEs. Severity is a measure of intensity (e.g., mild, moderate, or severe myocardial infarction). Seriousness is defined by the criteria under Section 12.2.1.2 and is based on subject/event outcome or action criteria usually

associated with events that pose a threat to a subject's life or functioning. An AE of severe intensity may not be considered serious. Assignment of an AE as 'Serious' (not severity) serves as a guide for defining regulatory reporting obligations.

13. OTHER STUDY ASSESSMENTS

13.1. Wechsler Abbreviated Scale of Intelligence, Second Edition

Wechsler Abbreviated Scale of Intelligence, Second Edition (WASI-II), is an abbreviated measure of cognitive intelligence designed for individuals 6 to 90 years of age. It is primarily used in clinical, psychoeducational, and research settings and was developed to quickly and accurately estimate cognitive intelligence when administration of a full battery is not feasible or necessary (McCrimmon and Smith 2012; Wechsler 2013).

The WASI-II should be administered and interpreted by a qualified rater with appropriate training and certification; the same person should administer and interpret the results of the measure. Nonverbal subjects will complete only the Perceptual Reasoning component of the WASI-II. For all subjects, a minimum IQ score of 65 is required for participation in the trial.

If feasible, and to minimize administration of this assessment where other criteria may exclude the subject, the WASI-II should be one of the final clinical assessments completed during Screening and as near as possible to Day 0. The WASI-II is provided in Appendix 7 and administration time is approximately 30-45 minutes.

14. DETERMINATION OF PLASMA NB-001 AND 4B-HYDROXYCHOLESTEROL CONCENTRATIONS

14.1. NB-001 Concentrations in Plasma

Blood samples for determination of NB-001 plasma concentrations will be collected at the time points noted in Table 3. On PK assessment days, the morning dose of NB-001 should be administered during the visit with the home health nurse.

NB-001 plasma concentrations will be compared between subjects, based upon dosing conditions, within this trial (i.e., subjects taking intact NB-001 capsules versus subjects taking NB-001 sprinkled on applesauce) and to historical data. Only PK samples collected during active NB-001 treatment for each subject will be analyzed after all subjects have completed the trial.

NB-001 concentration and other relevant data from this trial may be pooled with data from other studies for nonlinear mixed effects modelling and reported separately.

| Collection of Samples for Plasma Concentrations on Days 1, 14, 50, 63 | | Example Schedule |
|--|--|------------------|
| Pre-dose | Collect PK and 4B-hydroxycholesterol samples | 9:45 am |
| Administer Morning Dose | | 10:00 am |
| 1-hour Post-dose | Collect PK sample | 11:00 am |
| 4 hours Post-dose | Collect PK sample | 2:00pm |
| Administer Evening Dose | | 6:00 pm |

PK = pharmacokinetic(s)

14.2. 4B-Hydroxycholesterol Concentrations in Plasma

Blood samples for the determination of concentrations of 4β -hydroxycholesterol, an endogenous biomarker for CYP3A4 induction, will be collected pre-dose at the visits noted in Table 3. Changes, if any, in 4β -hydroxycholesterol concentrations 2 weeks after the start of IP in subjects assigned to active and placebo arms will be used in the assessment of CYP3A4 induction potential of NB-001.

14.3. Sample Handling

PK and 4β -hydroxycholesterol sample collection, processing, and shipping instructions will be provided separately in the Laboratory Manual.

15. STATISTICS

This section provides a summary of key reporting and statistical analytic methods of the trial data. A detailed description of these concepts, including modifications to the methods described below, will be given in the SAP and will be finalized before the database lock. Any deviations from the SAP will be reported in the clinical study report.

15.1. Analysis Sets

The following analysis sets will be used in the trial:

- Enrolled Analysis Set (ENR): The ENR consists of all subjects who meet all eligibility criteria and receive at least 1 complete daily dose (400 mg) of IP.
- Full Analysis Set (FAS): The FAS consists of ENR subjects who have at least 1 valid post-baseline efficacy evaluation within each treatment period. Subjects will be analyzed based on the treatment to which they were randomized. Subsets in the FAS are referred to as evaluable subjects.
- Safety Analysis Set (SAS): The SAS consists of all subjects who receive at least 1 capsule (100 mg) of IP. Subjects will be analyzed based on treatment received.
- Per Protocol Analysis Set (PPS): The PPS consists of FAS subjects who do not have major protocol deviations. Subjects will be analyzed based on the treatment received.

Efficacy analyses will be conducted using the FAS, with sensitivity analyses performed using the PPS.

15.2. General Procedures

Trial population and baseline data collection (e.g., subject disposition and demographics) will be presented by treatment sequence and for all subjects combined. Efficacy and safety endpoints will be summarized by treatment group.

Continuous variables will be summarized with descriptive statistics (number evaluated, mean, standard deviation, median, minimum, and maximum). Categorical variables will be presented as counts and percentages within each category. As appropriate, 95% confidence intervals will be included.

15.3. Sample Size

A total of 30 evaluable subjects, with 15 subjects in each treatment sequence, are planned for enrollment in this trial. The sample size is chosen to guarantee approximately 80% power for demonstrating a statistically significant treatment effect at a 2-sided alpha of 0.05 if the true mean difference (NB-001 versus placebo) for the CGI-I score at the end of each treatment period is 1 and the standard deviation is 1.25. This sample size calculation is based on the paired t-test.

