A total of 30 evaluable subjects are planned for enrollment in the trial: 15 subjects in each treatment sequence. 'Evaluable' is defined as having received at least 1 dose of IP and having at least 1 postbaseline efficacy evaluation within each treatment period. Assuming a 10% dropout rate, approximately 34 subjects will be randomized into the trial. With this sample size, the trial will have approximately 80% power to establish a statistically significant treatment effect at a 2-sided alpha of 0.05 if the true mean difference (NB-001 vs. placebo) for the primary efficacy endpoint (CGI-I score) is 1 and the standard deviation is 1.25. In the event the trial is updated based on another unspecified endpoint, the sample size may be increased accordingly.

Number of Subjects (Planned):

Approximately 34 subjects will be randomized; additional subjects may be enrolled, at the discretion of the Sponsor, to replace subjects who terminate early from the trial.

Diagnosis and Main Criteria for Inclusion: Subject Inclusion Criteria:

- 1. The subject has a genotype with a pathologic deletion in the 22q11 region confirmed by documentation (e.g., genetic test results) available at the clinical trial site.
- 2. The subject is aged 6 to 17 years old, inclusive.
- 3. The subject has a CGI-S scale score of ≥4 (i.e., moderately, markedly, severely, or among the most extremely ill patients) at Screening. Note that the Severity score of 4 could be from a composite of 2 or more sub-threshold scores.

And either:

- *a*. Psychiatric symptoms in the clinical range for **at least 1 of 3 disorders**, anxiety disorder, ADHD, or ASD, respectively, as demonstrated by score(s) at or above the following numbers *on at least 1 of 3 scales*:
 - PARS 5-Item Severity Score ≥ 12 (i.e., sum of items $2+3+5+6+7 \geq 12$)
 - ADHD-RS-5 Scores of 2 or 3 (i.e., "Often" or "Very Often") on at least 6 questions, with the majority of symptoms related to inattention (common in 22q11DS) rather than hyperactivity (less common in 22q11DS)
 - SRSTM-2 ≥ 60

OR:

- b. Psychiatric symptoms in the **subclinical range for at least 2 of 3 disorders**, anxiety disorder, ADHD, and/or ASD, respectively, as demonstrated by scores at or above the following numbers *on at least 2 of 3 scales*:
 - PARS 5-Item Severity Score of 10 or 11 (i.e., sum of items 2+3+5+6+7=10 or 11)

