15.4. Efficacy Analyses

All statistical testing will be based on a 2-sided significance level of 0.05 and will be considered exploratory in nature. Efficacy results will be analyzed by treatment group. Data collected at

post-baseline evaluation time points will be combined across the 2 treatment periods depending on the treatment received, based on the following:

The baseline value will be the last measurement reported prior to the first dose of any IP at Day 1 during Treatment Period 1 or Day 50 during Treatment Period 2 and will be further defined in the SAP.

The treatment effect on the continuous efficacy endpoints, i.e., CGI-I and CGI-S and other efficacy endpoints, will be evaluated using mixed-effects models. A model will be defined for each endpoint to include treatment, visit, treatment-by-visit interaction, period and sequence as fixed effects, subject nested within sequence as a random effect, and the baseline value as a covariate. The within-subject errors will be modeled using an unstructured covariance matrix. The Kenward-Roger approximation will be used to estimate denominator degrees of freedom. If a model fails to converge, other covariance structures will be evaluated until model convergence is met.

Each efficacy endpoint will be first evaluated within the subset of subjects with the corresponding significant domain/symptom of greatest impairment, e.g., the treatment effect on the PARS will be assessed within the subset where the symptom of greatest impairment is anxiety. Additional analyses of the efficacy endpoints will be performed in the overall subject population.

A supportive analysis of the efficacy endpoints measured on an ordinal scale, including the CGI-I and CGI-S will be performed by comparing the treatment groups using a Wilcoxon signed-rank test at each post-baseline evaluation.

An overall treatment effect evaluation will be performed using the global test for multiple endpoints (O'Brien 1984; Dmitrienko and Tamhane 2009). This test relies on pooling the evidence of effectiveness across several endpoints and will be employed for assessing the evidence to support the global alternative hypothesis that NB-001 is uniformly better than placebo in the mean changes in the PARS, ADHD-RS-5, and SRSTM-2 scores (treated as 1 instrument).

Efficacy summaries will be based on observed data only and no explicit imputation to account for missing data will be performed.

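### The stated power of about 80% with 30 subjects does not follow from the paired t-test inputs: they give about 99%, or 85% or more, depending on which standard deviation 1.25 is, and the plan does not say

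*Protocol*

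**What the plan says.** Protocol section 15.3 plans 30 evaluable subjects, 15 per sequence, and gives the reason: "The sample size is chosen to guarantee approximately 80% power for demonstrating a statistically significant treatment effect at a 2-sided alpha of 0.05". The effect assumed is a true mean difference between NB-001 and placebo which "for the CGI-I score at the end of each treatment period is 1 and the standard deviation is 1.25". The method is named: "This sample size calculation is based on the paired t-test". SAP section 4.6 repeats the same inputs, method and power.

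The Synopsis (Sample Size Justification) gives the same difference and SD, "for the primary efficacy endpoint (CGI-I score) is 1 and the standard deviation is 1.25", and states the result as a point value: "With this sample size, the trial will have approximately 80% power to establish a statistically significant treatment effect". It does not name the test. It defines an evaluable subject as one with at least one dose and at least one post-baseline efficacy evaluation in each period, and inflates 30 to about 34 for 10% dropout.

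No section says which standard deviation 1.25 is or gives a correlation between a subject's two periods. Protocol section 15.4 adds: "All statistical testing will be based on a 2-sided significance level of 0.05 and will be considered exploratory in nature".

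**The concern.** A paired t-test works on within-subject differences, so its power depends on the SD of those differences. Taken as that SD, 1.25 makes a 1-point difference 0.8 standard deviations. Thirty pairs are then far more than 80% power requires. Taken as the SD of the score in each period, it cannot give a power figure without a within-subject correlation, and none is stated.

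The power statement is the only quantitative justification for N. It tells the reader that a true 1-point CGI-I effect would be missed 20% of the time. If that figure is wrong, a reader of a null CGI-I result has a wrong idea of what the trial could have detected. The Synopsis also allows N to be increased if the endpoint changes, and any such recalculation needs a starting point that can be reproduced.

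**Working it through.** **Inputs** (Protocol 15.3, SAP 4.6): n = 30 pairs, difference δ = 1, SD 1.25, two-sided α = 0.05, paired t-test. Treating each evaluable subject as one pair follows the plan's own calculation.

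**Formula.** With SD_d the SD of within-subject differences, the noncentrality parameter is δ√n / SD_d on n − 1 degrees of freedom. Power is the probability that the noncentral t exceeds the two-sided critical value, which is 2.045 for 29 df.

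**Reading A: 1.25 is the SD of differences.**
- n = 30: noncentrality √30 / 1.25 = 4.38; power **98.8%**. With 28 df, to allow for a period term, it is still 98.8%.
- n = 15: √15 / 1.25 = 3.10; power 82.1%. n = 14 gives 79.0%. So 80% needs 15 subjects in total.
- Difference detectable with 80% power at n = 30: 0.66 points.

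**Reading B: 1.25 is the SD in each period.** Then SD_d = 1.25 × √(2(1 − ρ)), where ρ is the within-subject correlation. The plan gives no ρ, so a range is shown for n = 30:

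| ρ | SD_d | Power |
|---|---|---|
| −0.2 | 1.936 | 78.0% |
| −0.1 | 1.854 | 81.5% |
| 0 | 1.768 | **85.0%** |
| 0.2 | 1.581 | 91.7% |
| 0.3 | 1.479 | 94.7% |
| 0.5 | 1.250 | 98.8% |

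At ρ = 0 the noncentrality is √30 / 1.768 = 3.10 and the unrounded power is 84.95%. At that correlation 27 subjects give 80.8% and 26 give 79.2%, so 80% needs 27. The difference detectable with 80% power at n = 30 is 0.66 × √2 = 0.94 points. If 1.25 were instead a residual within-subject SD, SD_d would again be 1.25 × √2 = 1.768 and power 85.0%.

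**What would give 80%.** Solving for power 0.80 at n = 30 and δ = 1 gives SD_d = 1.89. If 1.25 is the per-period SD, ρ = 1 − 1.89² / (2 × 1.25²) = 1 − 3.57 / 3.125 = −0.14.

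**Other routes tried, to recover the plan's figure:**
- Normal approximation, Reading A: 99.2%.
- One-sided paired test: 99.6% (A) or 91.6% (B, ρ = 0).
- Two-sample t-test: 56.2% with 15 per group, 86.1% with 30 per group.
- All 34 randomized subjects, paired: 99.5% (A) or 89.3% (B, ρ = 0).

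None of these is within 2 points of 80%. The dropout step does reproduce: 30 / 0.9 = 33.3, rounded up to 34.

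**The case against.** The strongest reply is that the real defect is an unlabelled SD, and that under Reading B the gap is only about 5 points. The word chosen, "The sample size is chosen to guarantee approximately 80% power", can be read as a floor, and 85% meets a floor. A non-negative correlation is also this review's condition and is not documented. CGI-I is rated against Day 0 in Period 1 and re-anchored to Day 49 in Period 2, and change ratings from separate baselines need not correlate positively. Further, an evaluable subject needs only one post-baseline evaluation per period, while the calculation concerns end-of-period scores and nothing is imputed. Thirty evaluable subjects may therefore give fewer than 30 pairs, and 27 pairs at zero correlation give 80.8%.

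Part of this stands. The size of the error depends on a reading the documents do not settle, so both figures must be given, and 85% as a bound holds only for non-negative correlation. But the plan offers neither a negative correlation nor lost pairs as its reason. The Synopsis gives a point value, not a floor, and a floor would not explain choosing 30 when 15 or 27 would reach 80%. No reading makes 99% approximately 80%.

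The low-materiality argument also stands in part: safety is the primary objective, testing is exploratory, and N and the analyses need not change.

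**Conclusion.** The concern holds. On the stated inputs the power is 98.8% if 1.25 is the SD of differences, the quantity a paired t-test uses. It is 85.0% or more if 1.25 is the per-period SD and the correlation is not negative. The chance of missing a 1-point effect is then about 1%, or at most 15%, against the 20% implied. The difference detectable with 80% power is 0.66 points, or 0.94 at zero correlation, against the stated 1.

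The conclusion assumes 30 complete pairs and the named test. For non-negative correlation the error understates power, so it is no argument that the trial is too small. It should be corrected because it is the only justification given for N, but its effect on the trial is limited.

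**What to change.** Keep N. In the Synopsis, Protocol section 15.3 and SAP section 4.6, state which SD 1.25 is, give the assumed within-subject correlation if it is the per-period SD, and restate the power to match. Name the paired t-test in the Synopsis as well. Suggested text:

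- *If it is the SD of differences:* With 30 subjects who have an end-of-period CGI-I score in both periods, a two-sided 0.05 paired t-test has about 99% power for a mean difference of 1 (SD of within-subject differences 1.25); 80% power corresponds to a difference of about 0.66.
- *If it is the per-period SD:* With 30 such subjects, the test has about 85% power for a mean difference of 1 at zero within-subject correlation (per-period SD 1.25), or the figure for the correlation actually assumed.

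This wording counts subjects with end-of-period scores in both periods, which matches the quantity in section 15.3 but is narrower than the plan's definition of evaluable. The sentence giving 30 evaluable subjects should be aligned with it. The cost is a wording correction in three places, with no change to N, conduct or any analysis.

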15.4. Efficacy Analyses

All statistical testing will be based on a 2-sided significance level of 0.05 and will be considered exploratory in nature. Efficacy results will be analyzed by treatment group. Data collected at

post-baseline evaluation time points will be combined across the 2 treatment periods depending on the treatment received, based on the following:

The baseline value will be the last measurement reported prior to the first dose of any IP at Day 1 during Treatment Period 1 or Day 50 during Treatment Period 2 and will be further defined in the SAP.

The treatment effect on the continuous efficacy endpoints, i.e., CGI-I and CGI-S and other efficacy endpoints, will be evaluated using mixed-effects models. A model will be defined for each endpoint to include treatment, visit, treatment-by-visit interaction, period and sequence as fixed effects, subject nested within sequence as a random effect, and the baseline value as a covariate. The within-subject errors will be modeled using an unstructured covariance matrix. The Kenward-Roger approximation will be used to estimate denominator degrees of freedom. If a model fails to converge, other covariance structures will be evaluated until model convergence is met.

Each efficacy endpoint will be first evaluated within the subset of subjects with the corresponding significant domain/symptom of greatest impairment, e.g., the treatment effect on the PARS will be assessed within the subset where the symptom of greatest impairment is anxiety. Additional analyses of the efficacy endpoints will be performed in the overall subject population.

A supportive analysis of the efficacy endpoints measured on an ordinal scale, including the CGI-I and CGI-S will be performed by comparing the treatment groups using a Wilcoxon signed-rank test at each post-baseline evaluation.

An overall treatment effect evaluation will be performed using the global test for multiple endpoints (O'Brien 1984; Dmitrienko and Tamhane 2009). This test relies on pooling the evidence of effectiveness across several endpoints and will be employed for assessing the evidence to support the global alternative hypothesis that NB-001 is uniformly better than placebo in the mean changes in the PARS, ADHD-RS-5, and SRSTM-2 scores (treated as 1 instrument).

Efficacy summaries will be based on observed data only and no explicit imputation to account for missing data will be performed.

Additional details of analysis methods to be applied to the efficacy endpoints will be described in the SAP.

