4.4.4 Primary Efficacy Endpoint Analysis Methods

The primary estimand is the difference in means between treatment groups in the CGI-I scale per central rater for all subjects in the FAS. Data collected at post-baseline evaluation time points will be combined across the two treatment periods depending on the treatment received.

The null hypothesis to be tested is that there is no difference between Placebo and NB-001:

$$H_0$$
: $\mu_A = \mu_B$;

Where μ_A and μ_B represent the mean values for Placebo and NB-001, at the end of each respective treatment period. The alternate hypothesis to be tested is that the treatment group means differ:

$$H_1$$
: $\mu_A \neq \mu_B$;

The treatment effect will be evaluated using a mixed-effects model that includes treatment, visit, treatment-by-visit interaction, period, and sequence as fixed effects, subject nested within sequence as a random effect, and the baseline CGI-S value as a covariate. The within-subject errors will be modeled using an unstructured covariance

Confidential Page 19 of 28

matrix. The Kenward-Roger approximation will be used to estimate denominator degrees of freedom. If the model fails to converge, other covariance structures will be evaluated until model convergence is met.

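### The supportive signed-rank test on CGI-I and CGI-S leaves out the period effect that the main model adjusts for; a rank-sum test on period differences would restore it at little cost

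*Protocol*

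**What the plan says.** Protocol 15.4 evaluates every efficacy endpoint with a mixed model that includes "treatment, visit, treatment-by-visit interaction, period and sequence as fixed effects". SAP 4.4.4 repeats this for the primary efficacy endpoint, CGI-I by the central rater, with "treatment, visit, treatment-by-visit interaction, period, and sequence as fixed effects".

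For endpoints on an ordinal scale, including CGI-I and CGI-S, Protocol 15.4 adds a supportive analysis, "comparing the treatment groups using a Wilcoxon signed-rank test at each post-baseline evaluation". Neither period nor sequence enters that test.

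The readable SAP does not mention the signed-rank test, and SAP 4.7, which lists changes from the protocol, does not include it. SAP 4.4.6 (Additional Efficacy Endpoint Analysis Methods) is in the contents list but not in the text available for review, so what it says on this point is unknown.

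**The concern.** A supportive rank test is there to show whether the model's conclusion depends on treating a 7-point ordinal scale as continuous. It does that cleanly only if nothing else changes. Here the period adjustment is dropped too, so a disagreement between the two analyses could come from period rather than from the scale.

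A period effect is plausible. Entry requires a CGI-S of at least 4 at Screening, so regression to the mean would fall mostly in Period 1. CGI-I is also rated against Day 0 in Period 1 and against Day 49 in Period 2 (Protocol 11.1). Unequal sequences are possible: the readable text describes no blocking, the FAS requires a post-baseline evaluation in each period, and only observed data are used, so the split can differ by visit.

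**Working it through.** **The plan's own figure.** Protocol 15.3 and SAP 4.6 give "approximately 80% power for demonstrating a statistically significant treatment effect at a 2-sided alpha of 0.05", where the difference "is 1 and the standard deviation is 1.25", by a paired t-test. The planned number is "A total of 30 evaluable subjects, with 15 subjects in each treatment sequence". Exact noncentral-t power at n = 30 is 98.8% if 1.25 is the SD of within-subject differences, and 85.0% if it is a per-period SD with correlation 0 (SD of differences 1.25 × √2 = 1.768). The stated 80% needs an SD of differences of 1.89. The figure is therefore not reproduced. That is a separate matter and does not decide this point, but it means the reading of 1.25 is an assumption.

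**Inputs.** From the plan: two-sided alpha 0.05, effect 1, SD 1.25, 30 evaluable subjects. Assumed, because the documents give no values: 1.25 is the per-period SD; between-period correlation is 0.5, so the SD of differences is 1.25 × √(2 × (1 − 0.5)) = 1.25; the period shift s is 0, 0.5 or 1.0 points; an alternative effect of 0.6 is also tried.

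**How period enters.** Let θ be the benefit in points (lower scores are better), s the amount by which Period 2 scores exceed Period 1 scores on the same treatment, n1 the A/P and n2 the P/A sample size, and N = n1 + n2.

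- NB-001 minus placebo has mean −θ − s in A/P and −θ + s in P/A. Pooled, the mean is −θ − s(n1 − n2)/N and the variance is 1.25² + 4s²·n1·n2/N².
- Period 1 minus Period 2 has mean −θ − s in A/P and θ − s in P/A. The difference between sequences is −2θ. The shift s cancels at any split, and half the contrast is the treatment effect.

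**At 15/15.** The bias term is zero and the SD becomes √(1.25² + s²): 1.346 at s = 0.5 and 1.601 at s = 1.0. For θ = 1, the mean over its standard error falls from 1/(1.25/√30) = 4.38 to 1/(1.601/√30) = 3.42 at s = 1.0.

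**At unequal splits.** The fraction of the shift that becomes bias is (n1 − n2)/N: −4/30 = −0.13 at 13/17, 6/30 = 0.20 at 18/12, and 10/30 = 0.33 at 20/10. At 13/17 with θ = 1 and s = 1.0, the pooled mean is −1 + 0.133 = −0.867, the SD is √(1.5625 + 0.982) = 1.595, and the ratio is 0.867/(1.595/√30) = 2.98.

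**Simulation** (scores rounded and limited to 1–7; several thousand trials per setting):

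| Split, effect | Shift | Signed-rank power | Rank-sum power |
|---|---|---|---|
| 15/15, 1 | 0.5 | 96% | 97% |
| 15/15, 1 | 1.0 | 92% | 97% |
| 15/15, 0.6 | 0.5 | 60% | 65% |
| 15/15, 0.6 | 1.0 | 45% | 65% |
| 13/17, 1 | 1.0 | 81% | 97% |

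With correlation 0 instead, at 15/15 and effect 1, the figures are 78–80% versus 79–81% at shift 0.5 and 70–73% versus 79–81% at shift 1.0.

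The direction of imbalance matters. At 17/13 with the same sign of shift, the bias favours NB-001 and the signed-rank test shows no power loss.

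**Type I error.** At 15/15 the signed-rank test rejects in about 3.5% of null trials at shift 0.5 and about 1.5% at shift 1.0. At 17/13 and 13/17 it rejects in 2.9–5.0% over shifts 0 to 1.0, and at 18/12 in about 5%. At 20/10 it rejects in about 8% at shift 0.5 and 13–14% at shift 1.0. The rank-sum test stays near 5% throughout.

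**How likely is such a split?** Starting from 17/17, a 10% loss from 34 is 3.4 subjects. Even if four were lost, all from one sequence, the result is 17/13. Reaching 20/10 needs chance imbalance at randomisation or much heavier dropout. Under simple randomisation of 30 (an assumption), a split of 18/12 or worse has probability 0.36 and 20/10 or worse 0.10.

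**The case against.** The strongest reply is that little rests on this test. Protocol 15.4 sets "All statistical testing will be based on a 2-sided significance level of 0.05" and calls all testing exploratory; efficacy is a secondary objective; and this test only supports a model that already adjusts for period. SAP 4.4.5 also plans CGI-I and CGI-S (central rater) analyses separately by treatment period, where a period shift cannot enter, and plots by sequence. A signed-rank result distorted by period would be read beside all of these. That stands, and it sets the severity.

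Three stronger readings are tempting, and the documents do not support them:

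- A reader might infer that ordinary dropout will inflate the type I error. It will not: the worst case under the planned 10% loss from a balanced start is 17/13, where there is no inflation.
- A reader might take 45% versus 65% as the expected loss. That needs an effect of 0.6, which is not the plan's, and a period shift larger than that effect. At the plan's effect of 1 the same shift gives 92% versus 97%.
- A reader might call this the only rank-based check on the CGI scales. With SAP 4.4.6 unavailable, one can say only that no other appears in the readable text.

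**Conclusion.** The inconsistency is real: the main model adjusts for period and sequence, and the supportive rank test adjusts for neither. At the planned 15/15 split the signed-rank test remains valid but conservative, losing about 1 point of power at a half-point shift and about 5 points at a one-point shift for the plan's effect. At unequal splits it is also biased, in a direction set by which sequence is larger. Inflated type I error is a concern only near 20/10.

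The sizes rest on the assumed shift, correlation and reading of the SD; the direction follows from the algebra. This is a cheap improvement of low severity.

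**What to change.** In Protocol 15.4 and the SAP, replace the signed-rank test with a Wilcoxon rank-sum test comparing the two sequences on each subject's Period 1 minus Period 2 score at each matched visit (Days 14 and 63, 28 and 77, 42 and 91). Report half the Hodges-Lehmann shift as the period-adjusted treatment effect, with its confidence limits halved likewise. If SAP 4.4.6 repeats the signed-rank test, change it there, and record the change in SAP 4.7 before unblinding.

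The cost is a sentence or two of text and a different procedure call, with no new data or subjects. The replacement is not free in every case: with no period effect there is essentially no power loss at 15/15, but about 1–4 points at 18/12 and 2–6 at 20/10. Neither test protects against differential carry-over after the one-week wash-out.
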